10.1.7 CLINICAL MONITORING

Clinical site monitoring is conducted to ensure that the rights and well-being of trial participants are protected, that the reported trial data are accurate, complete, and verifiable, and that the conduct of the trial is in compliance with the currently approved protocol/amendment(s), with International Council for Harmonisation Good Clinical Practice (ICH GCP), and with applicable regulatory requirement(s).

- Monitoring for this study will be performed by an independent academic research organization (ARO; Johns Hopkins University, Division of Brain Injury Outcomes, Baltimore, MD).
- Remote, risk-based, monitoring will be employed for 100% data verification of endpoint, safety and other key data variables. On-site monitoring visits will be employed early, for initial assessment and training and then for-cause as needed.
- The investigator and IDE Sponsor will be provided copies of monitoring reports within 7 days of visit.
- Details of clinical site monitoring are documented in a Clinical Monitoring Plan (CMP). The CMP describes in detail who will conduct the monitoring, at what frequency monitoring will be done, at what level of detail monitoring will be performed, and the distribution of monitoring reports.

10.1.8 QUALITY ASSURANCE AND QUALITY CONTROL

Each clinical site will perform internal quality management of study conduct, data and biological specimen collection, documentation and completion. An individualized quality management plan will be developed to describe a site's quality management.

Quality control (QC) procedures will be implemented beginning with the data entry system and data QC checks that will be run on the database will be generated. Any missing data or data anomalies will be communicated to the site(s) for clarification/resolution.

Following written Standard Operating Procedures (SOPs), the monitors will verify that the clinical trial is conducted and data are generated and biological specimens are collected, documented (recorded), and reported in compliance with the protocol, International Council on Harmonisation Good Clinical Practice (ICH GCP), and applicable regulatory requirements (e.g., Good Laboratory Practices (GLP), Good Manufacturing Practices (GMP)).

The investigational site will provide direct access to all trial related sites, source data/documents, and reports for the purpose of monitoring and auditing by the sponsor, and inspection by local and regulatory authorities.

10.1.9 DATA HANDLING AND RECORD KEEPING

10.1.9.1 DATA COLLECTION AND MANAGEMENT RESPONSIBILITIES

Data collection is the responsibility of the clinical trial staff at the site under the supervision of the site investigator. The investigator is responsible for ensuring the accuracy, completeness, legibility, and timeliness of the data reported.

All source documents should be completed in a neat, legible manner to ensure accurate interpretation of data.

Hardcopies of study visit worksheets will be provided for use as source document worksheets for recording data for each participant enrolled in the study. Data recorded in the electronic case report form (eCRF) derived from source documents should be consistent with the data recorded on the source documents.

Clinical data (including adverse events (AEs), concomitant medications, and expected adverse reactions data) and clinical laboratory data will be entered into the VISION EDC system (Prelude Dynamics, Austin, TX), a 21 CFR Part 11-compliant data capture system provided by the Data Coordinating Center (Brain Injury Outcomes (BIOS) Division of Johns Hopkins University). The data system includes password protection and internal quality checks, such as automatic range checks, to identify data that appear inconsistent, incomplete, or inaccurate. Clinical data will be entered directly from the source documents.

10.1.9.2 STUDY RECORDS RETENTION

Study documents should be retained for a minimum of 2 years after the last approval of a marketing application in an International Council on Harmonisation (ICH) region and until there are no pending or contemplated marketing applications in an ICH region or until at least 2 years have elapsed since the formal discontinuation of clinical development of the study intervention.

No records will be destroyed without the written consent of the sponsor, if applicable. It is the responsibility of the sponsor to inform the investigator when these documents no longer need to be retained.

10.1.10 PROTOCOL DEVIATIONS

A protocol deviation is any noncompliance with the clinical trial protocol, International Council on Harmonisation Good Clinical Practice (ICH GCP), or Manual of Procedures (MOP) requirements. The noncompliance may be either on the part of the participant, the investigator, or the study site staff. As a result of deviations, corrective actions are to be developed by the site and implemented promptly.

These practices are consistent with ICH GCP:

- 4.5 Compliance with Protocol, sections 4.5.1, 4.5.2, and 4.5.3
- 5.1 Quality Assurance and Quality Control, section 5.1.1
- 5.20 Noncompliance, sections 5.20.1, and 5.20.2.

It is the responsibility of the site investigator to use continuous vigilance to identify and report deviations within 7 working days of identification of the protocol deviation, or within 7 working days of the scheduled protocol-required activity. All deviations must be addressed in study source documents and reported to the Data Coordinating Center via entry into the eCRF. Protocol deviations must be sent to the reviewing Institutional Review Board (IRB) per their policies. The site investigator is responsible for knowing and adhering to the reviewing IRB requirements. Further details about the handling of protocol deviations will be included in the MOP.

10.1.11 PUBLICATION AND DATA SHARING POLICY

This study will be conducted in accordance with the following publication and data sharing policies and regulations:

The funder (Biocompatibles UK Ltd.) will review the primary results manuscript prior to publication.

10.1.12 CONFLICT OF INTEREST POLICY

The independence of this study from any actual or perceived influence is critical. Therefore, any actual conflict of interest of persons who have a role in the design, conduct, analysis, publication, or any aspect of this trial will be disclosed and managed. Furthermore, persons who have a perceived conflict of interest will be required to have such conflicts managed in a way that is appropriate to their participation in the design and conduct of this trial. The study leadership has established policies and procedures for all study group members to disclose all conflicts of interest and will establish a mechanism for the management of all reported dualities of interest.

10.2 ADDITIONAL CONSIDERATIONS

None.

10.3 ABBREVIATIONS

| | |
|---------|--|
| ADE | Adverse Device Effect |
| AE | Adverse Event |
| ANCOVA | Analysis of Covariance |
| ASA | American Surgical Association |
| ASAT | Abdominal Subcutaneous Adipose Tissue |
| BAE | Bariatric Embolization |
| BEATLES | Bariatric Embolization of ArTeries with imaging visible EmbolicS |
| BES | Binge Eating Scale |
| BIS/BAS | Behavioral Avoidance/Inhibition Scales |
| BMI | Body Mass Index |
| BP | Blood Pressure |
| CBCT | Cone Beam Computed Tomography |
| CFR | Code of Federal Regulations |
| CLIA | Clinical Laboratory Improvement Amendments |
| CMP | Clinical Monitoring Plan |
| CO2 | Carbon Dioxide |
| COC | Certificate of Confidentiality |
| CONSORT | Consolidated Standards of Reporting Trials |
| CRF | Case Report Form |
| CT | Computed Tomography |
| CTA | Computed Tomography Angiogram |
| DCC | Data Coordinating Center |
| DHHS | Department of Health and Human Services |
| DNA | Genetic Material |
| DSMB | Data Safety Monitoring Board |
| DRE | Disease-Related Event |
| EC | Ethics Committee |
| eCRF | Electronic Case Report Forms |
| EGD | Esophagogastroduodenoscopy |
| EUC | Electrolytes Urea and Creatinine |
| EWL | Excess Weight Loss |
| FCI | Food-Craving Inventory |
| FDA | Food and Drug Administration |
| FDAAA | Food and Drug Administration Amendments Act of 2007 |
| FFR | Federal Financial Report |
| GCP | Good Clinical Practice |
| GERD | Gastroesophageal Reflux Disease |
| GHS | Growth Hormone Secretagogue |
| GHS-R | Growth Hormone Secretagogue Receptor |
| GI | Gastrointestinal |
| GLP | Good Laboratory Practices |
| GLP-1 | Glucagon-Like Peptide |
| GMP | Good Manufacturing Practices |
| GWAS | Genome-Wide Association Studies |
| HEENT | Head, Ears, Eyes, Nose, Throat |
| HIPAA | Health Insurance Portability and Accountability Act |
| HR | Heart Rate |
| IB | Investigator's Brochure |
| ICH | International Council on Harmonisation |
| ICMJE | International Committee of Medical Journal Editors |
| IDE | Investigational Device Exemption |
| IMAT | Intramuscular Adipose Tissue |
| IND | Investigational New Drug Application |
| IRB | Institutional Review Board |
| ISM | Independent Safety Monitor |
| ISO | International Organization for Standardization |

| | |
|---------|--|
| ITT | Intention-To-Treat |
| IWQOL | Impact of Weight on Quality of Life |
| LB | Pounds |
| LEAP2 | Liver-Expressed Antimicrobial Peptide 2 |
| LSMEANS | Least-squares Means |
| MedDRA | Medical Dictionary for Regulatory Activities |
| MES | Medical Effect Score |
| MITT | Modified Intention to Treat |
| MOP | Manual of Procedures |
| MRI | Magnetic Resonance Imaging |
| MSDS | Material Safety Data Sheet |
| NCT | National Clinical Trial |
| NIH | National Institutes of Health |
| NIH IC | NIH Institute or Center |
| NSAID | Nonsteroidal Anti-Inflammatory Drugs |
| NTE | Non Target Vascular Embolization |
| OHRP | Office for Human Research Protections |
| PI | Principal Investigator |
| PPY | Peptide YY |
| QA | Quality Assurance |
| QC | Quality Control |
| QOL | Quality of Life |
| RYGBP | Roux-en-Y Gastric Bypass |
| SADE | Serious Adverse Device Effect |
| SAE | Serious Adverse Event |
| SAP | Statistical Analysis Plan |
| SMC | Safety Monitoring Committee |
| SOA | Schedule of Activities |
| SOC | System Organ Class |
| SOP | Standard Operating Procedure |
| T | Temperature |
| TAT | Total Adipose Tissue |
| TFEQ | Three-Factor Eating Questionnaire |
| TLT | Total Lean Tissue |
| UP | Unanticipated Problem |
| US | United States |
| VAT | Visceral Adipose Tissue |

10.4 PROTOCOL AMENDMENT HISTORY

The table below is intended to capture changes of IRB-approved versions of the protocol, including a description of the change and rationale. A Summary of Changes table for the current amendment is located in the Protocol Title Page.

| Version | Date | Description of Change | Brief Rationale |
|---------|------|-----------------------|-----------------|
| | | | |
| | | | |
| | | | |
| | | | |
| | | | |
| | | | |

Appendix A: Post-Procedure Diet Plan (1 week)

Clear liquid diet (1-2 days)

A clear liquid diet consists of clear liquids — such as water, broth and plain gelatin — that are easily digested and leave no undigested residue in your intestinal tract.

Clear liquids and foods may be colored so long as you are able to see through them. Foods can be considered liquid if they are even partly liquid at room temperature. You can't eat solid food while on a clear liquid diet.

The following foods are allowed in a clear liquid diet:

- Water (plain, carbonated or flavored)
- Fruit juices without pulp, such as apple or white grape
- Fruit-flavored beverages, such as fruit punch or lemonade
- Carbonated drinks, including dark sodas (cola and root beer)
- Gelatin
- Tea or coffee without milk or cream
- Strained tomato or vegetable juice
- Sports drinks
- Clear, fat-free broth (bouillon or consomme)
- Honey or sugar
- Hard candy, such as lemon drops or peppermint rounds
- Ice pops without milk, bits of fruit, seeds or nuts

Any foods not on the above list should be avoided.

Once you can tolerate your clear liquid diet – you may progress to a:

Full liquid diet (1-2 days)

A full liquid diet is similar to a clear liquid diet, but you can also consume milk, vegetable juice, pureed soups and strained cooked cereals thinned with milk or water. Artificial sweeteners and liquid sweeteners are also allowed on a full liquid diet.

Foods Allowed on the Full Liquid Diet

- All kinds of fruits and vegetable juice
- Pureed fruit or vegetables
- Milk
- Soy or almond milk
- Yogurt (without fruit chunks)
- Melted cheese
- Eggs can be eaten as a soft custard
- Honey
- Syrup
- Coffee
- Tea
- Soft drinks
- Sports drinks
- Water
- Strained cooked cereal
- Broth
- Creamed soup (no pieces or chunks of vegetables or meats)
- Pureed meat can be added to soup (again, no chunks)
- Sugar
- Flavored gelatin
- Ice cream (no fruit, chocolate chips, etc.)
- Sorbet and frozen yogurt

Once you can tolerate your full liquid diet – you may progress to a:

Regular Diet as directed by the Weight Management Center

Once you advance to a regular weight loss diet, please avoid all sugary beverages – substitute with diet or sugar-free drinks. If in doubt – go with water!

1.0 Introduction

This document provides details of the statistical considerations, analyses, and reports planned for the Bariatric Embolization of ArTeries with imaging visibLe EmbolicS (BEATLES) trial. BEATLES is an investigator-initiated, prospective, double-blinded, randomized, sham-controlled study that will assess the impact of bariatric embolization on the systemic levels of obesity-related hormones and, as a consequence, on weight loss. The goal of this study is to help treat obesity combining a lifestyle program and a minimally invasive, angiographic approach.

All data collection procedures and statistical analyses in this SAP report are considered as final, and were finalized and approved by the Clinical Investigators and Sponsor prior to data lock. In addition, the data collection procedures and statistical analyses detailed in this SAP report may modify and are given precedence over the analytical plans outlined in the clinical protocol; however, any major modifications or change in the primary endpoint and/or its analysis will also be reflected in a protocol amendment.

2.0 CONSORT Diagram

A CONSORT diagram will be created as the trial progresses, and presented at each Data Safety Monitoring Board (DSMB) meeting and at other meetings as requested by the DSMB. This diagram will present a breakdown of patient disposition, and information presented in the figure will include: 1) the number of patients screened; 2) enrolled and randomized numbers; 3) patients who failed screening (along with a breakdown of reasons for trial exclusion); 4) patients removed from the analyses who were enrolled and/or randomized, but found to be ineligible post-randomization; and 5) patients who dropout or were lost-to-follow-up, and reasons for dropping out or lost, if known.

3.0 Study Design and Objectives

3.1 Design Overview

The BEATLES study is a prospective, phase 2, single-site, double-blinded, randomized, sham-controlled trial. Patients who meet all of the inclusion / exclusion criteria, and who consent to participate in the trial, will be randomized at a 1:1 ratio to receive either bariatric embolization surgery under CT guided imaging, or receive a sham procedure, which mimics the actual embolization surgery. Those patients randomized to the control arm will be given subcutaneous lidocaine and receive a skin nick on the wrist or groin, whichever area is pre-determined in the pre-anesthesia care unit by the operating physician. The sham arm is necessary in this trial to provide a control against which weight loss due to embolization can be compared. All patients in both arms will receive weight management support.

3.2 Randomization

If all eligibility criteria for the study have been met by a given patient, and the patient consents to participate in the study, then this patient will be randomized into one of the two treatment groups via a computer-generated randomization scheme. Additionally, stratified randomization by diabetic status will be utilized to remove its potential confounding effect in comparing weight loss between treatment arms. Upon randomization/enrollment, each patient will be assigned a unique numeric patient identity code. Once randomized, the patient will be scheduled for their assigned procedure, and will follow the steps of the procedure as outlined in the clinical protocol.

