6 STUDY INTERVENTION

6.1 STUDY INTERVENTION(S) ADMINISTRATION

6.1.1 STUDY INTERVENTION DESCRIPTION

This study is being conducted under IDE G190208 utilizing an investigational device, BTG-001933, which is a radiopaque embolic bead 100-200 µm (Biocompatibles UK, Ltd) intended to be used for bariatric embolization [of the left gastric and/or gastroepiploic arteries](#). The summary of test validation studies is on file with the FDA and available in the Investigator's Brochure.

Control Arm Procedures

Participants randomized to the control arm will follow the same screening and pre-procedure assessment, and will also take the same pre-procedure medications. After becoming eligible, participants will be scheduled for their procedure. On procedure day, the interventional radiologist will determine radial or groin access in the post-anesthesia care unit per local policy. After the participant and procedure area are prepped, and a basic tray is opened, all participants will be given standard moderate sedation medications. At this point, the participant will have a drape placed over a drape support above their face to limit their vision and be given ear plugs and noise-cancelling headphones to dampen their hearing, preventing them from seeing and hearing the procedure but still allowing them to keep in contact with the procedure team. The participant will be randomized to either the control or intervention arm using central randomization software. Participants randomized to the control arm will receive no other procedural intervention. The procedural team instead will follow a prescribed simulated protocol that will mimic an actual embolization procedure. All participants will receive subcutaneous lidocaine and a skin nick to their groin or their wrist as pre-determined by the operating physician in the pre-anesthesia care unit, including those randomized to the control arm. If the skin nick is on the wrist, the operating physician will close it with an external compression device, and if it is in the groin, the physician will hold pressure for at least 5 minutes.

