7.2 PARTICIPANT DISCONTINUATION/WITHDRAWAL FROM THE STUDY

Subjects are free to withdraw from participation in the study at any time upon request.

The DSMB will determine if stopping rules apply. Stopping rules that would necessitate withdrawal of any individual subject include development of any of the following conditions during the six-month period following the procedure. All efforts should be made to follow AEs to resolution or stabilization unless the subject withdraws consent:

- Development of gastric ulceration observed at the follow-up endoscopy that requires surgical therapy. If ulceration can be managed medically, it will be treated by a gastroenterologist, and the participant will remain in the study.
- Small bowel obstruction, hernia, small bowel incarceration, abdominal abscess, gastrointestinal bleed, hypotension, new onset cardiac ectopy, bradycardia, tachycardia, bowel perforation, pneumothorax, pneumonia, hypoxemia, azotemia, heart failure, CO₂ narcosis, ventricular bigeminy, pulmonary venous congestion, septicemia, shock, mesenteric venous thrombosis, deep vein thrombosis, pulmonary emboli, adhesions, or death.
- Subjects may also be removed from the study by the investigator for the following reasons:
 - Staying in the study would be harmful to the subject (this includes new pregnancy during follow-up).
 - The subject needs treatment that is not allowed in the study.
 - It is decided that another therapeutic approach can improve the subject's medical care.
 - The subject fails to follow instructions.
 - The subject is not complying with study visits.
 - The study is cancelled.
 - There may be other reasons to remove study subjects that are not known at this time.

The reason for participant discontinuation or withdrawal from the study will be recorded on the electronic Case Report Form (eCRF). Subjects who sign the informed consent form and are randomized but do not receive the study intervention may be replaced. Subjects who sign the informed consent form, and are randomized and receive the study intervention, and subsequently withdraw, or are withdrawn or discontinued from the study will not be replaced.

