8.2.15 Randomization

Data documenting demographic information, medical history, physical examination, medication and prior treatment, clinical labs, pregnancy test, and urinalysis will be reviewed against the eligibility criteria to determine eligibility. The determination will be recorded on the relevant eCRF.

If a patient is determined to be eligible to participate in the study, the patient will be randomized.

Randomization will be determined using assignment by a computer-generated randomization scheme. Upon randomization/enrolment, each patient will be assigned a unique numeric patient identity code.

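### SAP 3.2 randomises before the procedure is scheduled, whereas the protocol randomises on the table on procedure day; the two must be reconciled

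*SAP*

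**What the plan says.** SAP 3.2 makes eligibility and consent the trigger for allocation: "then this patient will be randomized into one of the two treatment groups via a computer-generated randomization scheme". It continues: "Once randomized, the patient will be scheduled for their assigned procedure". The same sentence ends by saying that the patient "will follow the steps of the procedure as outlined in the clinical protocol".

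Protocol 6.1.1 reads differently: "After becoming eligible, participants will be scheduled for their procedure". On procedure day the access site is determined, the participant is prepared, sedated and draped, and hearing is blocked. Only then does the text say: "The participant will be randomized to either the control or intervention arm using central randomization software". The Schedule of Activities (1.3) marks randomisation under Procedure Day. Protocol 8.1 makes eligibility, not allocation, the condition for scheduling that day.

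Protocol 8.2.15 says only: "If a patient is determined to be eligible to participate in the study, the patient will be randomized". It does not place this relative to scheduling or sedation.

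On exits between allocation and procedure, Protocol 7.2 states: "Subjects who sign the informed consent form and are randomized but do not receive the study intervention may be replaced". SAP 1.0 says that its data collection procedures and statistical analyses "may modify and are given precedence over the analytical plans outlined in the clinical protocol".

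**The concern.** On-table randomisation protects a sham-controlled trial because almost nothing can happen between allocation and procedure. SAP 3.2, read literally, opens an interval there of unstated length. Scheduling a patient for the assigned procedure also requires someone to know the assignment.

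The documents' own rules make that interval matter. A patient lost before allocation is a screen failure under Protocol 5.4 and does not disturb the comparison. The same patient lost after allocation is a randomised participant, whom the plan then excludes from key analysis sets and may replace. If the reasons for leaving differ by arm, the comparison is no longer between the groups as randomised.

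The primary endpoint is also timed from randomisation in some places and from the procedure in others. That is harmless only while both fall on one day.

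**Working it through.** **1. The two orders side by side.**

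| Step | SAP 3.2 | Protocol 6.1.1 |
|---|---|---|
| 1 | Eligible and consenting | Eligible |
| 2 | Randomised | Scheduled |
| 3 | Scheduled for the allocated procedure | Procedure day: access site, preparation, sedation, drape, hearing block |
| 4 | Procedure steps as in the protocol | Randomised, then embolisation or sham |

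The orders cannot both hold. Step 4 of the SAP column also sends the reader to steps that contain the randomisation, so the SAP sentence conflicts with the text it cites.

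**2. What would move to the wrong side of allocation under the SAP order.**
- The repeat pregnancy test (Protocol 8.2.6) is timed to the day of the procedure or the day before, and must be negative for the participant to continue. A test timed by the procedure date cannot come before that date is set, so it would fall after allocation.
- Laboratory tests more than 30 days old at the procedure are repeated to confirm eligibility (Protocol 1.3, 8.1). Some of these would also fall after allocation.
- Refusals and withdrawals before the procedure would become post-randomisation exits.

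**3. What the plan does with those exits.**
- SAP 4.1: the Full Analysis Set, used for efficacy, keeps only patients who undergo and complete the assigned procedure.
- Protocol 9.3: the mITT set excludes late-discovered ineligibility, participant refusal, investigator refusal to treat in the assigned arm, and withdrawal before exposure.
- Protocol 7.2: they may be replaced, with no rule for how the replacement is allocated.

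Only the protocol's ITT analysis (9.3) would keep them.

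**4. The clocks.** Protocol 9.1, Protocol 9.4.2 and SAP 5.3 time the primary endpoint from randomisation; SAP 3.5, 5.2 and 6.0 time it from the procedure. Safety is split in the same way (Protocol section 3 against 9.4.4). With a lag of L days and a ±14-day window at month 12, the two windows share 28 − L days. For example, with L = 15, a visit 10 days after the randomisation anniversary is 5 days before the procedure anniversary and lies inside both windows. A visit exactly on target by one clock leaves the other's window once L exceeds 14. The windows stop overlapping once L exceeds 28. No document gives L.

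**5. Size.** The plan's own sample size reproduces. With a difference of 8 − 3.3 = 4.7 kg, SD 7 kg and two-sided alpha 0.20, a noncentral-t calculation gives 80.9% power at 21 per arm, and 21/0.8 = 26.25, rounded up to 27. No exit rate is stated, so what follows is illustration on assumed inputs only.
- *Power.* Suppose 1 to 5 of 27 leave one arm before the procedure, are not replaced, and 20% of the rest drop out. That arm has (27 − k) × 0.8 = 20.8 to 17.6 evaluable, against 27 × 0.8 = 21.6 in the other. Power is 81.1% to 78.4%, compared with 81.7% when k = 0.
- *Bias.* Suppose the leavers' mean 12-month change would have differed from the stayers' by D = 2 to 7 kg. Excluding them shifts the arm mean by kD/27, from 1 × 2/27 = 0.07 kg to 5 × 7/27 = 1.30 kg. That is 2% to 28% of 4.7 kg.

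The exposure is to bias more than to loss of power.

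**The case against.** The strongest reply is that the protocol already settles the matter. Timing of allocation is trial conduct, whereas the SAP's precedence clause covers data collection and analysis. The protocol's Statement of Compliance bars changes to the protocol without FDA and IRB approval, and the SAP sentence itself defers to the protocol's steps. On this view SAP 3.2 is loose drafting that no site would follow. That largely stands, and it is why the harm is conditional. It does not remove the contradiction, and 8.2.15 does nothing to resolve it.

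A second reply is that exits after allocation, and their replacement, are allowed by Protocol 7.2 and 9.3 whatever the order, so correcting SAP 3.2 would not abolish them. This is also right. On-table randomisation shortens the interval without closing it, so the replacement rule needs its own sentence.

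A reader might infer that allocation concealment is lost. The documents do not support this. Allocation is computer-generated, and nothing in SAP 3.2 reveals the next assignment before a patient is entered. At most, some staff would learn the arm earlier. The procedural team is unblinded in any case, and no text says that participants would be told.

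A reader might also infer that embolisation patients would cancel more often than sham patients. No figure or statement in the documents shows this.

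**Conclusion.** The contradiction holds. SAP 3.2 states an order of allocation and scheduling that is the reverse of Protocol 6.1.1 and inconsistent with the Schedule of Activities. The consequence is conditional on the SAP order being followed. In that case the trial gains an avoidable interval in which eligibility failures and refusals become post-randomisation exits, which the plan's analysis sets and replacement rule handle badly, and the two 12-month clocks separate.

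The size of any bias cannot be derived. The ranges in the working rest on assumed exits and assumed outcome differences. Two figures that a reader might take as a magnitude should not be used as one. Each exit is 1/27 = 3.7% of an arm, but that is a share of the arm and not a bias. Nor does a lag above 14 days by itself put every month-12 visit outside the other clock's window, because some visits satisfy both until the lag exceeds 28 days. The sample size is unaffected.

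**What to change.** - **SAP 3.2:** replace the sentence with the protocol order: schedule, prepare and sedate, then release the allocation from the central system on procedure day.
- **Protocol 8.2.15:** cross-refer to 6.1.1 for the time point.
- **Both documents:** state that randomisation day is procedure day (Day 0) for all efficacy and safety endpoints, so that the two ways of timing 12 months are the same.
- **Protocol 7.2:** state that a replacement takes the next assignment on the list, and that the replaced participant stays in the as-randomised (ITT) analysis.
- **SAP 2.0:** report exits between randomisation and procedure by arm, with reasons, in the CONSORT diagram.

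The cost is wording in the SAP and a short protocol amendment. On-table randomisation is already the protocol's design, so no visit, procedure or sample size changes.
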